Protocol Cover Page

Protocol Title: Development and Validation of a Cloak Shaped Device for Sham Pediatric Tuina

NCT Number: NCT03474172

Protocol Date: April 20, 2018

Version: Version 3 (final)

Principle [name] M.D.

Investigator

Leading [name] 2nd Affiliated Hospital of Guangzhou University of Chinese Medicine

Authors [name] 2nd Affiliated Hospital of Guangzhou University of Chinese Medicine

Other [name] Guangzhou University of Chinese Medicine

Authors [name] 2nd Affiliated Hospital of Guangzhou University of Chinese Medicine

[name] 2nd Affiliated Hospital of Guangzhou University of Chinese Medicine

[name] Dongguan Kanghua Hospital

[name] Guangzhou University of Chinese Medicine

[name] Dongguan Kanghua Hospital

[name] Guangzhou University of Chinese Medicine

Abstract

Background: With the overwhelming acceptance of evidence-based medicine, valid placebo device or placebo procedure become one of the key issues for randomization and placebo-controlled design clinical trials on the validation of treatment modalities. However, few have been developed for Pediatric Tuina (PT) which is a therapeutic massage for children. Blinding both the recipients and the clinical researcher is considered essential for good research practice. Up to now, no well recognized placebo device or procedure for PT has been reported. We developed a Cloak Shaped Device (CSD) , and design a RCT to detect whether the device is effective as a placebo in PT researches.

Methods: This is a two-arm, parallel-group RCT, while participants and researchers will be blinded. Sixty eligible children will be randomly assigned to genuine Tuina or sham Tuina group with the informed consent signed by their guardians. During the process of Tuina, a CSD will be used to cover the children's body so that the children, guardians, observers and researchers will be blinded. Guardians and observers will be asked to ascertain whether they could differentiate genuine Tuina from sham Tuina. The primary outcomes are the accuracy judgment rates based on guardians' and observers' evaluations of the type of Tuina that participants actually received.

Discussion: This study will contribute to the development of a valid placebo device which can be applied in RCTs regarding pediatric Tuina.

Keywords: placebo procedure; device; sham control; Pediatric Tuina; Chinese pediatric massage.

Background

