The aim of this study is to evaluate the validity of CSD whether it may have a balanced accurate rate (e.g. 50%) on the type of Tuina that the child actually received in the genuine or sham group, when judged by guardians and observers, respectively. About 95% of the subjects can distinguish the genuine and sham pediatric Tuina accurately without placebo device in the clinical practice. Based on the results from the previous similar researches, an ideal blinding device will be considered have

a good blinding effect while the accurate rate of subjects (genuine group or sham group) on guessing the Tuina type is 50%. Therefore, we adopt the single-sample test in the software of PASS 11.0 (NCSS LLC) to calculate the sample size, and set accurate rate of subjects with 95% in non-blinding status, and 50% in blinding status, powered by 90%, and significance level with 0.05. After the calculation, 24 subjects of each group are needed, on account of the 20% subject may drop out, the finally sample size is 60 subjects in total with 30 subjects in each group.

Development of the CSD

The CSD is made of opaque cotton cloth in cloak-shape. It is big enough to cover the upper body, including upper limbs and trunk, of a child who is 6 year-old or under old. Two narrow holes are present for therapists to insert their hands through and perform Tuina. The entire manipulation process will be covered by the CSD. Blinding will be maintained during the whole study process.

Genuine pediatric Tuina and sham pediatric Tuina

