The study will respect the Helsinki declaration. It has been approved by the ethics committee of Guangdong Provincial Hospital of Chinese Medicine(Z2017-212-01) and DongGuan Kanghua Hospital(2018003), and has been registered on the ClinicalTrials.gov (Identifier: NCT03474172)before the recruitment of subjects. Informed consent must be endorsed by one guardian of each child if the child is going to attend the trial. All the participants will receive a bonus for the traffic when they complete the trial.

Statistical analysis

All the data in this study will be recorded in a case report form (CRF). When the trial is complete, data will be entered into the database by double entry method. We will use Wilcoxon rank sum test analysis for abnormal distribution data, Mann-Whiney U test for ranked outcomes and chi-squared test for binary outcomes.

In the primary outcome, we will calculate accurate judgment rates on type of Tuina the participants received by guardians and observers, respectively.

In the secondary outcomes, Mann-Whiney U test will be used for the comparison of Verbal Rating Scale (VRS) of parent's attitude towards pediatric Tuina, VRS of Children's Perception of Pediatric Tuina, VRS of Parent's Attitude Towards Pediatric Tuina from the Observers' Perspectives, Compliance of guardians and children in terms of three continuous PT therapies between groups.

Simple Kappa Coefficient will be used to analysis the agreement of the judge results and the attitude towards PT between the guardians and observers. We will use Chi-square test to identify the influence factor, including the education level, age, Children's Perception, parent's attitude, et al.

Statistical Packages of Social Sciences (SPSS) for Windows version 18.0 (Chicago, IL) will be used to conduct the analyses. For all tests, two-tailed P value less than 0.05 is considered as statistically significant.

The Kappa coefficient ranges from 0 to 1.0. In the study, we define if the coefficient value is less than 0.2, it presents that the agreement is slight. If it ranges from 0.21-0.40 indicates the agreement is weak; ranging from 0.41-0.60 means the agreement is moderate; ranging from 0.61-0.80 implies the agreement is favorable. And for those range from 0.81-1.00 it represents that the agreement is perfect.

Quality monitoring

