All the researchers will be trained before the trial conducted, including the communication skills with guardians and children, subjects screening, randomization and evaluation procedure. Meanwhile, three experienced therapists will receive a well-designed session of manipulation technical training course to reach a high level of standardization. Detail information on dropout, adverse event of subjects will be recorded on the CRF. During the study period, supervisors will check the CRF aperiodically.

Discussions

To our knowledge, this trial is the first study aiming for the validity of a placebo device in regards of sham PT. On the basis of a rigorous randomized controlled design of our study, the results may provide

evidence for CSD on whether it is worthy to be applied as a useful placebo device for the evidence-based researches of pediatrics when PT or other similar massage interventions will be adopted.

Despite PT, other non-pharmaceutical therapies of Chinese Medicine have developed some sham or blinding methods, such as several types of sham acupuncture or sham cupping devices. The effects of these methods have been revealed by adopting similar research design as this study[16,21-23].

PT has been found to be easily accepted by children based on the light and gentle technique with good safety record. Up to now, none severe adverse event due to PT was reported, some mild adverse events such as skin abrasion can be easily avoided with clear and correct operating instructions. Therefore, guardians and children are very likely to have good compliance to complete the trial. We assume children less than 6 years old cannot differ the genuine PT and sham PT when they are lack of former experience of PT, and consequently the placebo effect for both groups will not be generated systematically. In this case, guardians' and observers' judgements will be more important than children's own perspective in the validation evaluation of the CSD.

In conclusion, this trial may provide valuable evidence on placebo device for the future RCTs in terms of PT or other similar kinds of massage.

Declarations

Ethics approval and consent to participate

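### The plan names about 50% accuracy as the mark of good blinding, but the 95% versus 50% sizing comparison cannot show it and the analysis specifies no comparison with 50%, interval or rule

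*Combined protocol and SAP*

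**What the plan says.** The Sample size section sets the aim as "whether it may have a balanced accurate rate (e.g. 50%) on the type of Tuina that the child actually received", judged by guardians and by observers. It describes an ideal device as one with "a good blinding effect while the accurate rate of subjects (genuine group or sham group) on guessing the Tuina type is 50" per cent. It puts accuracy without any device at about 95%, and sizes the trial on a single-sample test with these settings: "set accurate rate of subjects with 95% in non-blinding status, and 50% in blinding status, powered by 90%, and significance level with 0.05". It does not say which rate is the null. The result is 24 per group, raised to 30 for 20% dropout.

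For the two primary outcomes the Statistical analysis section says: "In the primary outcome, we will calculate accurate judgment rates on type of Tuina the participants received by guardians and observers, respectively". Its general list of methods gives "Mann-Whiney U test for ranked outcomes and chi-squared test for binary outcomes", and it adds: "For all tests, two-tailed P value less than 0.05 is considered as statistically significant". The 50% figure does not appear there. Kappa is planned for agreement between guardians and observers, and chi-square for influence factors; neither sets accuracy against chance.

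The Abstract says the investigators "design a RCT to detect whether the device is effective as a placebo in PT researches". The Discussions section expects the results may give "evidence for CSD on whether it is worthy to be applied as a useful placebo device".

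**The concern.** The question is whether accuracy is close enough to 50% for the cloak to serve as a sham. The sizing comparison asks something else. With 95% as the null, rejection shows only that accuracy is below its level without the cloak. With 50% as the null, the hoped-for result is non-rejection, which a small sample can produce even when the cloak blinds poorly.

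The analysis text does not close the gap. The chi-squared test could be applied to either of two tables that answer different questions, and nothing says how the rates lead to a conclusion. The judgement on validity would therefore be made after the data are seen, and later sham-controlled trials of pediatric Tuina could rest on it.

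**Working it through.** **Inputs.** From Sample size: 95%, 50%, power 90%, alpha 0.05, 24 evaluable and 30 enrolled per group. From Statistical analysis: two-tailed 0.05. Assumed: one guardian and one observer judgement per child, independent across children (the number of observers is not stated), and equal evaluable arms.

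**The plan's own figure.** One-sample formula: n = (z_α√(p0q0) + z_β√(p1q1))² / (p0 − p1)².
- Null 95%, two-sided: (1.960×0.2179 + 1.2816×0.5)²/0.45² = 1.1405/0.2025 = 5.6, so 6.
- Null 50%, two-sided: (1.960×0.5 + 1.2816×0.2179)²/0.45² = 1.5858/0.2025 = 7.8, so 8.
- Exact versions need 7 to 12.

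So 24 does not follow from the named test. A two-group comparison with continuity correction gives 23, but that is not the method named. The dropout step does reproduce: 24/0.8 = 30. The mismatch is a separate matter; 24 and 30 are taken as given below.

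**If 95% is the null** (exact binomial, lower tail 0.025). P(X≤19 | 24, 0.95) = 0.006 and P(X≤20) = 0.030, so the limit is 19. P(X≤25 | 30, 0.95) = 0.016 and P(X≤26) = 0.061, so the limit is 25.

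| | n=24 | n=30 |
|---|---|---|
| Highest count that rejects 95% | 19 (79%) | 25 (83%) |
| Exact 95% CI | 58-93% | 65-94% |
| P(reject), true 75%, one arm | 0.75 | 0.90 |
| P(reject), true 75%, both arms | 0.753² = 0.57 | 0.902² = 0.81 |
| P(reject), true 80%, one arm | 0.54 | 0.74 |

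**If 50% is the null** (exact, two-sided). Rejection needs X≤6 or ≥18 of 24, or X≤9 or ≥21 of 30. At a true 70%, non-rejection in one arm has probability 0.61 (n=24) or 0.41 (n=30). The highest non-rejecting counts are 17/24 (CI 49-87%) and 20/30 (CI 47-83%). These intervals include 50%, but also much higher accuracy.

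**The two chi-squared tables** (full enumeration, no continuity correction, all-correct tables counted as non-significant). Let a_G and a_S be accuracy in the genuine and sham arms.
- Judgement by allocation tests P(judged genuine | genuine) = a_G against P(judged genuine | sham) = 1 − a_S. Equality means a_G + a_S = 1, that is, average accuracy of 50%. If nobody can discriminate but 70% guess genuine in both arms, it is significant with probability 0.052 (n=24 per arm) or 0.049 (n=30).
- Accuracy by arm tests a_G = a_S. At 95% accuracy in both arms it is non-significant with probability 0.98 or 0.97. In the 70%-guess-genuine case (accuracy 70%/30%, no discrimination) it is significant with probability 0.84 or 0.90. It gives the wrong signal in both cases.

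**Precision available** (exact 95% CI at an observed 50%). Per arm: 12/24, 29-71%; 15/30, 31-69%. Over both arms: 24/48, 35-65%; 30/60, 37-63%.

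**Illustration with assumed limits.** The documents give none. Suppose the CI for pooled accuracy had to lie within 30-70%. At a true 50%, this is met with probability 0.53 (48 evaluable) or 0.75 (60) per rater group. Searching even totals, 0.90 is first reached at 78 (0.91); it dips to 0.899 at 84 and is above 0.90 again at 86. Applied by arm, about 78 would be needed in each arm, or 2×78 = 156 in all.

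**The case against.** The strongest reply is that the judgement is binary, the plan assigns chi-squared to binary outcomes, and the natural table is judgement by allocation. That table does test chance-level discrimination, as the algebra shows. This stands. A reader might infer that the plan has no route to a test of chance accuracy; the text does not support that. What it supports is that the table is unspecified, so chance may or may not be tested. Even on the favourable reading, a non-significant result would not prove good blinding.

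A second reply is that the plan never commits to declaring the cloak valid from a rejected 95% or a non-significant test. It gives 50% only as an example, promises calculated rates, and says the results may provide evidence. This also stands. A reader might infer that such a declaration is planned; the documents only leave it open. Readers could also compute intervals from the reported rates, but that does not supply a prespecified basis for the conclusion.

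A third reply is that unequal arm accuracies, such as 70%/30% or 80%/20%, should not be counted as blinding failure. That is right. With pooled accuracy near 50%, such a split is a preference for one guess without discrimination. The per-arm rates describe it; they are not a second test of discrimination.

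**Conclusion.** The point holds in this form: the 95% versus 50% comparison, and the 90% power attached to it, support at most a statement that the cloak is better than no cloak. The analysis section does not say how accuracy will be compared with 50%. A cloak with a true accuracy of 75% would still reject 95% in one arm with probability 0.75 to 0.90. The accuracy-by-arm table would almost always be non-significant with the blind essentially absent in both arms.

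A reader might also infer that the trial is too small and must enrol more children. The documents do not support that: they state no limits around 50%, so no required size follows, and the figures of 78 and 156 rest wholly on assumed limits.

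The probabilities rest on independent judgements, one per rater type per child. If the same observers judge many children, the intervals could be wider. With unequal evaluable arms, pooled accuracy would no longer be the simple average of the two arm rates.

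**What to change.** 1. In Sample size, label the null. State that the 95% versus 50% comparison and its power support at most better than no cloak, and that a non-significant test is not evidence of adequate blinding.
2. In Statistical analysis, make the primary report, for guardians and for observers separately, accuracy over both arms with an exact 95% CI set against 50%, as the measure of discrimination. Beside it, give accuracy in each arm with its CI to show guessing preference. State that a split such as 70%/30% or 80%/20% with pooled accuracy near 50% will be reported as guessing preference without discrimination. Specify that any chi-squared test is of judgement by allocation.
3. Limit the conclusion to the estimates and their intervals, unless the sponsor prespecifies and justifies limits on both sides of 50%.

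**Cost.** Wording only, on data the plan already collects; enrolling more children is not part of the fix. The downside is a more modest conclusion. Even an observed 50% would be reported with an interval of 35-65% (48 evaluable) or 37-63% (60) over both arms, and wider in each arm.

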We will use the randomized controlled design to assess the validity of the CSD for sham PT. The primary outcomes are the accuracy judgement rates based on guardians' and observers' evaluations of the type of Tuina that participants actually received.

One of the guardians for each child will be informed with all the information of the trial before the child is included. They will be told that their children may receive genuine PT or sham PT. Once the informed consent signed, eligible children will be randomly assigned to genuine PT or sham PT group with 1:1 ratio. Computer generated randomization lists will be concealed in the opaque envelopes, which performed by irrelevantly authorized expert from the department of medical statistics of The 2nd Affiliated Hospital of Guangzhou University of Chinese Medicine.

Trained practitioners will manually do 15 minutes session of Tuina on each participant while the guardians and observers are watching. The guardians and observers will be required to record their judgements of the type of Tuina, either it is genuine or sham PT, that the participant actually received. If the child is equal to or older than 3 years old, researchers will ask the child some questions in terms of the experience of Tuina after they finish the Tuina procedure.

Study population

Children will be recruited at the outpatient department of pediatrics in Dongguan Kanghua hospital which is a tertiary A western medicine hospital located in Dongguan, Guangdong province, China.

Inclusion criteria:

- Children with disease in Pediatric Outpatient Department of Kanghua Hospital
- Children aged 0-6 years.
- Guardian and child can be cooperative over the study period.
- Guardian signed the informed consent.
- Children have no attendance in other studies simultaneously.

Exclusion criteria:

- Child with one or more PT experiences on arms, abdomen or back.
- Child with a previous history of convulsion.
- Child with any of the following conditions on the area to be manipulated: phlebitis, open wound, fracture and tissue damage.
- Child combined with any of following conditions: disorders of consciousness, seizures or twitching, shock, varicella, hand-foot-mouth disease, encephalitis B, and etc.

Sample size

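### The named single-sample calculation (95% against 50%, 90% power, alpha 0.05) does not give 24 per group; the exact test needs 9 to 12

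*Combined protocol and SAP*

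**What the plan says.** The Sample size section of the combined protocol and SAP gives the method, "we adopt the single-sample test in the software of PASS 11.0 (NCSS LLC) to calculate the sample size", and the rates, "set accurate rate of subjects with 95% in non-blinding status, and 50% in blinding status", with 90% power and a significance level of 0.05. The result is "After the calculation, 24 subjects of each group are needed, on account of the 20% subject may drop out", which leads to 30 per group and 60 in total. The section does not say which rate is the null, whether the test is exact or approximate, or whether it is one- or two-sided.

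The same section sets the standard for a successful device. It is judged to have "a good blinding effect while the accurate rate of subjects (genuine group or sham group) on guessing the Tuina type is 50" per cent.

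The Statistical analysis section fixes the sidedness: "For all tests, two-tailed P value less than 0.05 is considered as statistically significant". For the primary outcome it says only: "In the primary outcome, we will calculate accurate judgment rates on type of Tuina the participants received by guardians and observers, respectively". It lists a chi-squared test for binary outcomes in general, but gives no null value and does not tie that test to the primary outcome.

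**The concern.** A gap of 45 percentage points, with one rate close to 1, is very large for a one-sample test of a proportion. Such a test should need roughly ten subjects, not 24. If 24 does not follow from its inputs, a reader cannot reproduce the sample size, and the named test, the power and the number cannot all be right.

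The contrast also matters for what the trial can claim. The aim is accuracy near 50%, but the calculation only separates 50% from 95%. Evidence that accuracy is below 95% is not evidence that it is near 50%. A reader who takes the 90% power at face value may think the trial was sized to show good blinding.

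**Working it through.** **Inputs.** From the Sample size section: rates 0.95 and 0.50 (difference d = 0.45), power 0.90, alpha 0.05, 24 evaluable per group, 20% dropout. From the Statistical analysis section: two-sided tests. The null is not stated, so each rate was tried in that role.

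**1. The dropout step.** 24 / (1 − 0.20) = 30 per group, 60 in total. This reproduces, so the fault lies in the 24.

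**2. Exact one-sample binomial test.** Two-sided 0.05 with equal tails: reject when either tail probability under the null is at most 0.025. Power is the probability of the rejection region under the other rate.

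| n | Power, null 95%, true 50% | Power, null 50%, true 95% |
|---|---|---|
| 8 | 0.855 | 0.663 |
| 9 | 0.910 | 0.929 |
| 10 | 0.945 | 0.914 |
| 11 | 0.967 | 0.898 |
| 12 | 0.981 | 0.980 |
| 24 | 0.9992 | 0.9999 |

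With null 95%, 90% power is reached at 9 and kept from there. With null 50%, it is first reached at 9, dips just below at 11, and is kept from 12. Against these, 24 is 24/12 = 2.0 to 24/9 = 2.7 times too large.

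**3. Normal approximations**, two-sided (z = 1.960 and 1.282):

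- n = [(1.960·√(p0(1−p0)) + 1.282·√(p1(1−p1))) / d]² gives 5.6 for null 95% and 7.8 for null 50%.
- With continuity correction, (n/4)·[1 + √(1 + 2/(n·d))]² gives 7.7 and 9.9.
- With one variance throughout, (1.960 + 1.282)²·p(1−p)/d² gives 13.0 with the variance at 0.50 and 2.5 with it at 0.95.

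**4. Other settings.** One-sided exact tests hold 90% power from 9 (null 95%) or 8 (null 50%). One-sided normal versions give 2.0 to 10.6. Over all one-sample variants at alpha 0.05, n rounds up to between 3 and 13. Even a two-sided exact test at alpha 0.001 needs only 14 to 19.

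**5. A different test.** Comparing two independent groups at 95% and 50% gives 18.5 per group by the pooled z formula and 22.7, so 23, with continuity correction. That is close to 24, but it is not the named test, and no group is treated without the cloak.

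**6. What the contrast shows about the 50% target.** With the equal-tails test, the largest counts that still reject 95% from below, with their Clopper-Pearson 95% intervals, are:

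- n = 24: 19 correct (79%), interval 58% to 93%.
- n = 30: 25 correct (83%), interval 65% to 94%.

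Both intervals exclude 50%. If true accuracy were 75%, 30 children would reject 95% with probability P(X ≤ 25) = 0.90.

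**7. What the planned numbers deliver at an observed 50%** (Clopper-Pearson 95% intervals):

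| Judgements | Correct | Interval |
|---|---|---|
| 24 (one arm, after dropout) | 12 | 29% to 71% |
| 30 (one arm) | 15 | 31% to 69% |
| 48 (pooled, after dropout) | 24 | 35% to 65% |
| 60 (pooled) | 30 | 37% to 63% |

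**The case against.** The strongest reply is that the error is on the safe side. At 24 the power target is exceeded, no child or procedure is affected, and 60 need not change. That is true, and it limits the seriousness of the point. It does not make the paragraph correct.

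A second reply is that 24 may come from a correctly run two-group calculation whose method was misnamed. The documents cannot settle this. A two-group origin is conjecture, and the nearest result is 23. If it were right, the paragraph would still name the wrong test. The safest description of the fault is that 24 cannot be reproduced as described.

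A third reply is that the plan nowhere says rejecting 95% proves good blinding, so 19 of 24 is not a trial decision rule. This stands. The example shows only the limit of the contrast used for the sample size. The count also depends on the version of the test: a minimum-likelihood exact test would reject at 20 of 24 as well (p = 0.030).

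Finally, precision at 50%, pooling and independence would be issues even if 24 were right. That is fair. They enter here because a corrected paragraph needs some valid justification for 30 per group. Whether an interval of 31% to 69% is narrow enough is for the investigators to argue.

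**Conclusion.** The concern holds. With the stated inputs the two-sided exact one-sample test needs 9 to 12 per group, not 24, and exact power at 24 is 0.9992 or 0.9999, not 0.90. No choice of null, sidedness or approximation that was tried at alpha 0.05 exceeds 13. The discrepancy is conservative for 95% against 50%, so this should be fixed but does not threaten the trial's size. The larger consequence is that the paragraph gives no assurance about the 50% target, for which one arm of 30 gives an interval of about 19 percentage points either side.

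The interval widths assume independent judgements. That is reasonable for guardians, one per child. For observers it is unknown: the Study design section says "The guardians and observers will be required to record their judgements of the type of Tuina", but the documents do not say how many observers there are or how many children each one judges.

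**What to change.** Keep 60 children and change the wording of the Sample size section.

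1. State the PASS procedure and settings that produced 24 (null value, exact or approximate test, sidedness), or correct the figure.
2. Remove or correct the 90% power claim for the single-sample test. At 24 per group the exact power for 95% against 50% is above 0.999.
3. Justify 30 per group by precision for the 50% target, per arm first. Suggested text: *With 30 (24 evaluable) children per group, an observed accuracy of 50% in one group has an exact 95% confidence interval of 31% to 69% (29% to 71%).* Give pooled accuracy only as a supplement, because it can hide opposite errors: if everyone guesses genuine Tuina, the arms score 100% and 0% and the pooled rate is 50%.
4. State that these widths assume independent judgements, and that they apply to observers only if each child's observer judgement is independent of the others.

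The cost is protocol wording only. Enrolment, procedures and data collection do not change.

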All the techniques and acupoints will be the same in both group, the only difference is that on whose skin that the manipulation will be performed. For Genuine PT the manipulation will be performed on the children's skin directly. However, in the Sham PT group, the therapist will put their own hand above the same skin areas as those in the Genuine PT group and do the Tuina with the other hand of their own. Five acupoints located on the upper limbs and the trunk are involved in both Tuina group, including Neibagua, Banmen and Dachang on hands, Fu on the abdomen, and Qijiegu on the sacroiliac region. The frequency of the techniques are as normal with 150 times per minute for Neibagua, 200 times per minute for Banmen, Dachang, and Qijiegu, 80 times per minute for Fu. The acupoints, manipulation time and frequency are the same for all subjects in two groups. All manipulations will be carried out with light, fast, and soft touch, and coconut oil will be used to protect children's skin in both groups.

Effective measurements

Primary Outcome Measures

- Accurate judgement rate of the guardians' estimation
- Accurate judgement rate of the observers' estimation

Secondary Outcome Measures

- Verbal Rating Scale (VRS) of parent's attitude towards pediatric Tuina (We use the VRS-4 with the higher score representing the more positive attitude to evaluate the degree of the awareness and reliability of the parents towards pediatric Tuina.)
- VRS of Children's Perception of Pediatric Tuina (Verbal Rating Scale, VRS). (We use the VRS-4 with the higher score representing the more positive attitude to evaluate the degree of the perception of the children equal or more than 3 years old during and after the Tuina.)
Children equal or more than 3 years old in both genuine Tuina and sham Tuina groups will evaluate their sensation, such as pain, warm, discomfort, itch, et al.
- VRS of Parent's Attitude Towards Pediatric Tuina From the Observers' Perspectives. (Verbal Rating Scale, VRS)(We use the VRS-4 with the higher score representing the more positive attitude to evaluate the degree of the reliability of the parents towards pediatric Tuina from the observers' perspectives.)

- Compliance of guardians and children on three continuous PT therapies. (Verbal Rating Scale, VRS)(We use the VRS-5 with the higher score representing the more positive attitude to follow three continuous PT therapies.)

Ethics

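### The kappa scale has the wrong range and labels zero or negative agreement as slight; a weighted kappa for the VRS-4 attitude rating would be a cheap addition

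*Combined protocol and SAP*

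**What the plan says.** The Statistical analysis section names one agreement statistic for two comparisons: "Simple Kappa Coefficient will be used to analysis the agreement of the judge results and the attitude towards PT between the guardians and observers". It gives the scale as "The Kappa coefficient ranges from 0 to 1.0" and sets verbal bands. At the bottom, "if the coefficient value is less than 0.2, it presents that the agreement is slight". The next band reads "If it ranges from 0.21-0.40 indicates the agreement is weak", and the bands continue upward to 1.00. There is no label for zero or negative values, no confidence interval for kappa and no weighted kappa. The section does not say whether kappa is computed over both arms together or within each arm.

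Under Secondary Outcome Measures, the guardian and observer attitude ratings are both four-level ordered scales: "We use the VRS-4 with the higher score representing the more positive attitude". The guardian item is described as being used "to evaluate the degree of the awareness and reliability of the parents towards pediatric Tuina". The observer item is used "to evaluate the degree of the reliability of the parents towards pediatric Tuina", as seen by the observer, with no mention of awareness.

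**The concern.** Kappa compares observed agreement with the agreement expected by chance, so zero means chance and negative values mean worse than chance. A scale that starts at zero, with an open-ended bottom band called slight, gives such results the name of a degree of agreement.

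In many trials this would be academic. Here it is not, because the Sample size section treats 50% accuracy as the mark of good blinding. If the device works and the two raters guess independently, their judgement kappa centres on zero.

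The attitude rating raises a different question, which is not an error. Simple kappa counts only exact matches. On a four-level ordered scale it scores a one-step difference and a three-step difference alike, so it cannot show whether guardian and observer nearly agreed.

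**Working it through.** **Range and bands.** Kappa = (po - pe)/(1 - pe), where po is observed and pe is chance agreement. Take 60 pairs (the planned total, assuming one guardian and one observer per child) with both raters splitting 30/30. Then pe = 0.5, and with *a* agreements kappa = (a/60 - 0.5)/0.5 = a/30 - 1.

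| Agreements of 60 | Kappa | Label under the plan |
|---|---|---|
| 0 | -1.00 | slight |
| 24 | -0.20 | slight |
| 30 | 0.00 | slight |
| 34 | 0.13 | slight |
| 36 | 0.20 | none: not below 0.2, not in 0.21-0.40 |

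The plan's stated minimum of 0 is therefore not reproduced. The value -1 is reached only with balanced margins, but negative values do not need them.

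**How often kappa is at or below zero.** Assumptions: each rater says genuine with probability 0.5 or 0.7, and a fraction *s* of the observer's guesses is shared with the guardian. The pair counts are 60 (planned total) and 48 (24 per group, the number before the 20% dropout allowance). The last column covers separate analysis by arm, with 30 or 24 pairs. Ranges span both guessing probabilities and both pair counts.

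| Shared fraction s | P(kappa ≤ 0), 60 or 48 pairs | P(kappa ≤ 0), 30 or 24 pairs |
|---|---|---|
| 0 | 0.51 to 0.52 | 0.52 to 0.54 |
| 0.1 | 0.23 to 0.27 | 0.32 to 0.36 |
| 0.2 | 0.06 to 0.10 | 0.15 to 0.21 |
| 0.3 | 0.01 to 0.03 | 0.06 to 0.10 |
| 0.4 | about 0.005 or less | 0.01 to 0.04 |

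Under independence the central 95% of kappa values is about -0.25 to 0.25 at 60 pairs. Small positive and small negative values therefore cannot be told apart, which is why a confidence interval is needed beside any label.

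**Simple against weighted kappa on four levels.** Take two constructed tables of 60 pairs, all margins 15, each with 32 exact agreements. Chance agreement is 0.25, so simple kappa = (32/60 - 0.25)/0.75 = 0.38 in both. Linear-weighted kappa = 1 - (mean observed step difference)/(mean expected step difference). With uniform margins the expected difference is (6×1 + 4×2 + 2×3)/16 = 1.25.

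- Table A, all 28 disagreements one step: mean difference 28/60 = 0.467, and 1 - 0.467/1.25 = **0.63**.
- Table B, 16 one-step, 10 two-step and 2 three-step: mean difference (16 + 20 + 6)/60 = 0.70, and 1 - 0.70/1.25 = **0.44**.

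The same simple kappa thus covers two different patterns. These tables are contrived. In a latent-normal model with correlation 0.3 to 0.85, linear kappa exceeds simple kappa by 0.07 to 0.18. When that model is matched to a simple kappa of 0.38, linear kappa is about 0.56 with uniform margins and 0.51 with margins of 5/15/40/40%. Both lie between the two constructed values.

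**The case against.** The stated range cannot be defended, but several points can be made about how much it matters.

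- **Low stakes.** Kappa is not a listed primary or secondary outcome, and no decision about the device hangs on a band. This stands, and it is why the error is graded minor.
- **The number would still be visible.** The plan defines words for values and does not say that the word replaces the coefficient. Slight is also already the lowest label. Both are true. Even so, a prespecified rule that names -0.20 a form of agreement should not be left in place.
- **Zero or negative kappa may be rare.** Guardians and observers watch the same session and may pick up the same cues. The working shows how quickly the probability falls with sharing. It remains appreciable at 10% to 20%, and is higher if kappa is computed by arm.
- **Weighting is a preference.** Simple kappa is valid for exact agreement, and in the latent model it is the lower figure, so it does not flatter. Linear weights assume equal steps, and the wording of the four categories is not given. Nor does the Mann-Whitney comparison of arms oblige the plan to weight: under "We will use Chi-square test to identify the influence factor, including the education level, age", the list goes on to include parental attitude as a factor. All of this stands, so weighting is offered as an addition only.
- **The constructed tables overstate the likely contrast.** This is fair. The model-based figures give a better idea of the usual gain.

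**Conclusion.** The point holds in both parts, at different strengths.

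The range and the bands are wrong as written, whatever is assumed about the raters. Nothing elsewhere in the document corrects them. The size is minor: the reporting of a supporting analysis is affected, and the primary accuracy rates and Mann-Whitney comparisons are not. How often the faulty label would apply does rest on assumptions: one observer per child (the Study design section gives no number), the degree of shared guessing, and pooling of the arms. It is about half of trials under independence and a few percent or less at 30% sharing in the pooled analysis.

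The weighted kappa is an improvement and does not correct an error. Whether the two attitude items measure the same thing is a point to confirm; the wording difference alone does not show a fault.

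**What to change.** 1. Confirm first that the guardian and observer attitude items are meant to rate the same thing. If they are not, no choice of weights makes their kappa meaningful.
2. State the range as -1 to 1. Label values at or below 0 as no agreement beyond chance. Make the bands continuous: above 0 to 0.20, above 0.20 to 0.40, and so on.
3. Report every kappa with its 95% confidence interval and number of pairs, and say whether it is pooled or by arm.
4. Keep simple kappa for the genuine/sham judgement.
5. For the VRS-4 attitude rating, prespecify a linear-weighted kappa before the data are seen, and show simple kappa beside it as the measure of exact agreement.

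The cost is mainly wording, with no new data. The drawback is that verbal labels depend on the weights: Table A gives 0.38 simple, 0.63 linear and 0.81 quadratic, which fall in three different bands. The coefficient and its interval should therefore be read before the label. The document does not show whether the named SPSS 18.0 procedure produces a weighted kappa, so this should be confirmed or other software named.
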